8.3.3.3 Expectedness

We expect that gastrointestinal symptoms (including fever, aspiration, belching, bloating, nausea or vomiting, gastroesophageal reflux, abdominal cramps, abdominal pain, diarrhea, constipation) may be common post administration of the investigational products, both as a consequence of the underlying disease being treated, and potentially as an adverse effect of the administered product.

In the initial, 60-minute bedside observation period following administration of investigational product, subjects will be monitored with close attention to the following:

- allergic reaction (temperature, skin rash, heart rate, or blood pressure change as already described)
- sepsis or shock (temperature, heart rate, or blood pressure change as already described)
- bowel injury (abdominal pain change)
- aspiration (respiratory rate or oxygen saturation change)
- gastrointestinal symptoms (belching, bloating, nausea, vomiting, GERD, abdominal cramps, abdominal pain, diarrhea, and constipation)

In the subsequent, 7-day monitoring period following administration of investigational product, subjects will be monitored with close attention to the following:

- donor-derived infection (temperature or abdominal pain change)
- gastrointestinal symptoms (aspiration, belching, bloating, nausea, vomiting, GERD, abdominal cramps, abdominal pain, diarrhea, and constipation)

In the subsequent, 28-, 48-, and 180-day monitoring periods, subjects will be monitored with close attention to the following:

- transmitted infection (temperature or abdominal pain change as already described)
- metabolic changes (polydipsia, polyuria, weight gain, or weight loss)

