8.1.2 Visit 1: Treatment

At this visit, the study coordinator will collect the one-week BM diary and stool sample from the subject. The PI or another trained physician will meet with the patient. Vital signs will be done to document temperature, blood pressure, heart rate, and oxygen saturation. A nasogastric tube will be placed and secured. The subject will then be escorted to the radiology suite by the study coordinator. A chest x-ray will be performed to ensure adequate placement of the nasogastric tube. The PI or trained physician will confirm adequate placement of the tube with the attending radiologist. The subject will then be escorted back to the office suite by the study coordinator. The PI or trained physician will then administer the treatment. The PMT-002 product will be drawn into a syringe and the syringe will be connected to the nasogastric tube (NGT) and the product will be pushed into the tube until all of the FMT product is administered. The NGT will then be removed by the PI or trained physician. The subject will remain in the office for one hour following the administration of the PMT product.

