8.1.5 Visit 3 (12 weeks post treatment)

Participants will return to the office for visit 3, twelve weeks (\pm 7 days) after the FMT treatment. The clinical research coordinator will collect final one-week BM diary as well as the stool sample (if available). This visit may occur via telemedicine or telephone, and samples provided via mail or drop off at the clinical site. The following questionnaires will be completed:

- Medication Log
- Adaption Index
- PFIQ-7
- SF-12
- PFDI-20
- ABLe Questionnaire
- FIQL
- Bristol Stool Index
- St. Mark's Score
- PGSC
- Global Impression Improvement
- PACSYM
- AE/SAEs

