8.2 Safety and Other Assessments

For all women of childbearing potential, a urine pregnancy test will be performed prior to FMT and at all subsequent study visits. If a subject's urine pregnancy test is positive prior to treatment with FMT, the subject will be removed from the study. It is recommended that women not become pregnant as it is unknown how this treatment will effect pregnancies. If a subject does become pregnant on study, the pregnancy will be followed.

To monitor for signs of infection subjects will be required to keep a temperature log for 7 days following FMT (a digital thermometer will be provided). Subjects will be instructed to call the study doctor if their temperature rises above 100.4 degrees or drops below 96 degrees. The study doctor will phone triage patients reporting elevated temperatures and bring them in for a study visit or direct them to the emergency room if necessary.

Subjects will also be provided with a card for the collection of all solicited adverse events in their study diary. The card will be reviewed with the diary for any adverse events.

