8.3.5 Time Period and Frequency for Event Assessment and Follow-Up

Safety will be assessed by monitoring and recording potential adverse effects using the Common Toxicity Criteria version 5.0 (CTCAE V5.0) at each study visit or participant contact (phone call/email). Participants will be monitored by medical histories, physical examinations, and

baseline status. If CTCAE V5.0 grading does not exist for an adverse event, the severity of mild, moderate, severe, life-threatening, and death, corresponding to Grades 1-5, will be used whenever possible.

At each contact with the subject, the investigator will seek information on adverse events by nondirective questioning and, as appropriate, by examination. Adverse events may also be detected when they are volunteered by the subject during the screening process or between visits, or through physical examination, laboratory test, or other assessments. Additionally, the subject study diary will include a card for the collection of all solicited adverse events. Information on all adverse events will be recorded in the source documentation. To the extent possible, adverse events will be recorded as a diagnosis and symptoms used to make the diagnosis recorded within the diagnosis event.

As much as possible, each adverse event or follow-up information will be evaluated to determine:

- 1. Severity grade (CTCAE V5.0 Grade 1-5)
- 2. Duration (start and end dates)

3. Relationship to the study treatment or process – [Reasonable possibility that an AE is related: No (unrelated/ not suspected) or Yes (a suspected adverse reaction)]. If yes (suspected) - is the event possibly, probably, or definitely related to the investigational treatment?

4. Expectedness to study treatment or process – [Unexpected – if the event, severity, and/or frequency is not described in the investigator brochure (if applicable) or protocol].

5. Action taken with respect to study or investigational treatment or process (none, dose adjusted, temporarily interrupted, permanently discontinued, unknown, not applicable).

6. Whether medication or therapy taken (no concomitant medication/non-drug therapy, concomitant medication/non-drug therapy).

7. Whether the event is serious.

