8.3.8 Stopping/Halting Rules

A study wide pause of PMT administration will be instituted if one of the following occur:

- Death attributable to FMT
- Suspected transmission of infection from donor to patient
- If two (2) or more subjects experience the same Grade 3 or higher AE
- If two (2) or more subjects experience an SAE related to the study product
- There is an increase in frequency of long-term adverse events (e.g., IBD, metabolic disease) in > two (2) FMT treatment subjects

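### Section 8.3.3.3 promises close attention to temperature, weight and metabolic symptoms out to day 180, but nothing schedules or solicits weight or metabolic symptoms after FMT, and the text describes no temperature recording after day 7

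*Combined protocol and SAP*

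**What the plan says.** Section 8.3.3.3 (Expectedness) sets out three stages of safety monitoring: the bedside hour, the first 7 days, and the later period. For the last it states: "In the subsequent, 28-, 48-, and 180-day monitoring periods, subjects will be monitored with close attention to the following". Two items follow: "transmitted infection (temperature or abdominal pain change as already described") and "metabolic changes (polydipsia, polyuria, weight gain, or weight loss").

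The operational sections say this:

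- **Section 8.1.2, Visit 1:** "Vital signs will be done to document temperature, blood pressure, heart rate, and oxygen saturation". Section 8.1.2.1 repeats vital signs at 30 and 60 minutes and adds respiratory rate. Neither mentions weight.
- **Section 8.2:** "subjects will be required to keep a temperature log for 7 days following FMT". The log is reviewed at Phone Contact 1 (Section 8.1.3) and handed in at Visit 2 (Section 8.1.4).
- **Sections 8.1.4 and 8.1.5, Visits 2 and 3:** questionnaires, medication log and AE/SAE review, with no vital signs or weight. Both visits may be remote. For Visit 3: "This visit may occur via telemedicine or telephone, and samples provided via mail or drop off at the clinical site".
- **Section 8.1.6, Phone Contact 2:** an adverse-event interview at day 180, by telephone or in person.
- **Section 8.3.5:** at each contact "the investigator will seek information on adverse events by nondirective questioning". The sentence goes on to allow examination where appropriate.
- **Section 8.3.8:** one ground for a study-wide pause is "There is an increase in frequency of long-term adverse events (e.g., IBD, metabolic disease) in > two (2) FMT treatment subjects".

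Section 2.3.1 lists metabolic change and weight change among the theoretical long-term risks.

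**The concern.** The section on expectedness commits to watching named late signals, but the visit sections, which tell staff what to collect, do not list how most of them would be obtained. Weight gain or loss is the clearest case, because a change needs a reading before and a reading after, and no later reading is scheduled.

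Safety is a primary objective in Section 3, and Section 4.1 says the pilot is to supply safety data for a later randomised trial. If weight and metabolic symptoms are neither measured nor asked about, their absence from the adverse-event tables cannot be told apart from their not having been looked for. That affects what the study can report about risks the protocol itself names.

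**Working it through.** **Step 1. Each promised late item against the text that could supply it after day 7.**

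- *Weight gain or loss.* Weight appears in the protocol text as a theoretical risk (Section 2.3.1) and in the Section 8.3.3.3 list, never as a scheduled measurement. The abbreviated physical at screening (Section 8.1.1) may include it, but its content is not given and no later reading would pair with it. Scheduled post-FMT weights named in the text: 0, for all 15 planned women.
- *Polydipsia and polyuria.* The solicited events named in Section 8.1.2.1 are aspiration and gastrointestinal symptoms. No metabolic item is among them. Later adverse-event inquiry is nondirective.
- *Temperature change.* Section 8.3.3.3 refers back to methods already described. Those are the treatment-visit vital signs and the 7-day log. Visits 2 and 3 list no vital signs.
- *Abdominal pain.* This is on the solicited list in Section 8.1.2.1, and the one-week diary issued at Visit 2 again carries the solicited-event card (Section 8.1.4). This item is partly covered.

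**Step 2. The Schedule of Activities.** In the extracted table in Section 1.3, the Temperature Log row shows marks under screening, Week 4 and Week 12. The table is visibly broken. The Week 4 mark fits return of the log at Visit 2. A screening mark does not fit a log issued after FMT, and Section 8.1.5 gives no support for a Week 12 mark. The row does not displace the explicit 7 days in Section 8.2, but it should be checked against the source, as should the vital-signs and symptom-review rows in the Section 1.2 table, whose columns are lost.

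**Step 3. The stated periods against the contacts.**

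- Visit 2: 4 × 7 = day 28; window 28 ± 7 = days 21 to 35.
- Visit 3: 12 × 7 = day 84; window 84 ± 7 = days 77 to 91.
- Phone Contact 2: day 180 ± 7 = days 173 to 187 in Section 1.3; ± 10 = days 170 to 190 in Section 8.1.6.

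The plan's 28 and 180 are reproduced. Its 48 is not: it falls 48 − 35 = 13 days after the Visit 2 window closes and 77 − 48 = 29 days before the Visit 3 window opens. If 48 is a transposition of 84 (an assumption), all three figures match the scheduled contacts exactly. That would settle the day-48 point only and leave Step 1 unchanged.

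**The case against.** The strongest reply is that adverse-event follow-up is continuous. Section 8.3.6 runs reporting from consent to 180 days, Section 8.1.8 says each visit looks back over the interval since the last one, and Section 8.3.5 allows examination as well as questions. Staff who have read Section 8.3.3.3 know which signals to look for. The adverse-event forms and the diary card are not in the documents, so they might carry metabolic prompts. All of this stands, and it means follow-up is not absent. It does not supply a paired weight, and open questioning is a weak instrument for gradual change.

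A reader might draw four stronger conclusions, which the documents do not support:

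- *That a weight change is seen only if a woman volunteers it.* Section 8.3.5 also provides for examination, though none is listed after FMT and the visits may be remote.
- *That the pause rule has no input.* Section 8.3.8 names diseases, not weight, and diagnosed metabolic disease would reach the sponsor through AE/SAE review. What is missing is any scheduled measurement that feeds the rule.
- *That 173 of 180 days (180 − 7; 96%) is a shortfall in temperature data.* Daily readings to day 180 were never promised, so this is not a measured deficit.
- *That a day-48 visit is missing.* The text speaks of monitoring periods, Visit 3 covers that interval, and 48 is probably 84.

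**Conclusion.** The protocol contradicts itself on late safety ascertainment, and the passages need to be reconciled. Weight and metabolic symptoms, which it names as long-term risks and as signals for close attention, have no scheduled or solicited ascertainment after FMT: 0 planned post-FMT weights, and no metabolic item among the named solicited events. For temperature, the text describes no recording after the 7-day log, subject to the check of the Week 12 mark in the schedule. Abdominal pain is partly covered.

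The consequence is limited but real. Reported events and diagnosed disease can still be captured at Week 4, Week 12 and day 180, but a statement of no metabolic signal at 180 days would be weakly supported. This should be put right; it does not undermine the trial. The day-48 discrepancy is clerical.

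The conclusion assumes that the undisclosed forms and diary card contain no metabolic prompts beyond those in the text, and that the visit lists in Sections 8.1.4 and 8.1.5 are complete.

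**What to change.** Reconcile Section 8.3.3.3 with the tables in Sections 1.2 and 1.3 and with Sections 8.1.4 to 8.1.6, 8.2 and 8.3.5. Either of two routes removes the contradiction, and the choice of monitoring is the sponsor's:

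1. Add the items Section 8.3.3.3 already names to the data collected at existing contacts: a baseline and a follow-up weight, self-reported when the contact is remote, and its named symptoms asked directly on the Visit 2, Visit 3 and Phone Contact 2 forms. Enter these in the Schedule of Activities, and tabulate directly asked items apart from spontaneously reported ones.
2. Revise Section 8.3.3.3 to describe what is actually collected, and limit any long-term metabolic safety statement to spontaneously reported events.

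Under either route, state how temperature is ascertained after day 7, explain or remove the Week 12 Temperature Log mark if the source shows it, and correct or explain the 48.

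The cost is a wording amendment and, under the first route, a weight reading and a few form questions at contacts that already exist. No new visits are needed. The small downside is that remote weights would be self-reported. The second route costs only text, but gives up part of the safety information that the pilot is meant to supply.

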8.3.4 Adverse Events of Special Interest

Any gastrointestinal symptom or allergic reaction adverse event grade 3 or higher will be classified as an adverse event of special interest. These events may be related to the use of the FMT product and should be recorded as an adverse event of special interest and reported to the sponsor. Reporting of Adverse Events of Special Interest should follow the reporting pathway described for Serious Adverse Events.

8.3.5 Time Period and Frequency for Event Assessment and Follow-Up

Safety will be assessed by monitoring and recording potential adverse effects using the Common Toxicity Criteria version 5.0 (CTCAE V5.0) at each study visit or participant contact (phone call/email). Participants will be monitored by medical histories, physical examinations, and

baseline status. If CTCAE V5.0 grading does not exist for an adverse event, the severity of mild, moderate, severe, life-threatening, and death, corresponding to Grades 1-5, will be used whenever possible.

At each contact with the subject, the investigator will seek information on adverse events by nondirective questioning and, as appropriate, by examination. Adverse events may also be detected when they are volunteered by the subject during the screening process or between visits, or through physical examination, laboratory test, or other assessments. Additionally, the subject study diary will include a card for the collection of all solicited adverse events. Information on all adverse events will be recorded in the source documentation. To the extent possible, adverse events will be recorded as a diagnosis and symptoms used to make the diagnosis recorded within the diagnosis event.

As much as possible, each adverse event or follow-up information will be evaluated to determine:

- 1. Severity grade (CTCAE V5.0 Grade 1-5)
- 2. Duration (start and end dates)

3. Relationship to the study treatment or process – [Reasonable possibility that an AE is related: No (unrelated/ not suspected) or Yes (a suspected adverse reaction)]. If yes (suspected) - is the event possibly, probably, or definitely related to the investigational treatment?

4. Expectedness to study treatment or process – [Unexpected – if the event, severity, and/or frequency is not described in the investigator brochure (if applicable) or protocol].

5. Action taken with respect to study or investigational treatment or process (none, dose adjusted, temporarily interrupted, permanently discontinued, unknown, not applicable).

6. Whether medication or therapy taken (no concomitant medication/non-drug therapy, concomitant medication/non-drug therapy).

7. Whether the event is serious.

Once an adverse event is detected, it should be followed until its resolution or until it is judged to be permanent, and assessment should be made at each visit (or more frequently, if necessary) of any changes in severity, the suspected relationship to the study treatment, the interventions required to treat it, and the outcome.

8.3.6 Adverse Event Reporting

Reporting period

Adverse events will be reported from the time of informed consent until study completion (180 days).

Investigator reporting: notifying the study Sponsor

Every SAE, regardless of suspected causality (e.g., relationship to study product(s) or study procedure(s) or disease progression) must be reported to the Sponsor within **24 hours** of learning of its occurrence.

Recurrent episodes, complications, or progression of the initial SAE must be reported to the Sponsor as a follow-up to the original episode within 24 hours of the investigator receiving the follow-up information. A SAE considered completely unrelated to a previously reported one should be reported separately as a new event.

Send the SAE report to the Sponsor.

New information regarding the SAE will be reported as it becomes available and in the same manner that the initial SAE (i.e. SAE form). The investigator must follow the event to resolution or until the event is deemed and documented irreversible, whichever is longer.

Investigator Reporting: Local Reporting Requirements

The investigator will report AEs and SAEs to the IRB of record and other local regulatory groups per the local requirements.

8.3.7 Serious Adverse Event (SAE) Reporting

The study clinician will immediately report to the Sponsor any serious adverse event, whether or not considered study intervention related, including those listed in the protocol or investigator brochure and must include an assessment of whether there is a reasonable possibility that the study intervention caused the event. Study endpoints that are serious adverse events (e.g., all-cause mortality) must be reported in accordance with the protocol unless there is evidence suggesting a causal relationship between the study intervention and the event (e.g., death from anaphylaxis). In that case, the investigator must immediately report the event to the Sponsor.

New information regarding the SAE will be reported as it becomes available and in the same manner that the initial SAE (i.e. SAE form). All serious adverse events (SAEs) will be followed until satisfactory resolution or until the site investigator deems the event to be chronic or the participant is stable. Other supporting documentation of the event may be requested by the study Sponsor and should be provided as soon as possible.

```
FMT for FI
IRB#: 834196
```

The SAE reports to the Sponsor should be sent to the pharmacovigilance coordinator.

In addition, all unexpected fatal or life-threatening suspected adverse reactions will be reported to the FDA as soon as possible but in no case later than 7 calendar days after the Sponsor's initial receipt of the information. Other SAEs that are both, unexpected and related to the study drugs (SUSAR) will be reported to the FDA as soon as possible but no later than 15 calendar days after knowledge of the event.

Investigator Reporting: Local Reporting Requirements

The investigator will report AEs and SAEs to the IRB of record and other local regulatory groups per the local requirements.

8.3.8 Stopping/Halting Rules

A study wide pause of PMT administration will be instituted if one of the following occur:

- Death attributable to FMT
- Suspected transmission of infection from donor to patient
- If two (2) or more subjects experience the same Grade 3 or higher AE
- If two (2) or more subjects experience an SAE related to the study product
- There is an increase in frequency of long-term adverse events (e.g., IBD, metabolic disease) in > two (2) FMT treatment subjects

8.3.9 Unanticipated Problems

8.3.9.1 Definition of Unanticipated Problems (UP)

The Office for Human Research Protections (OHRP) considers unanticipated problems involving risks to participants or others to include, in general, any incident, experience, or outcome that meets all of the following criteria:

• Unexpected in terms of nature, severity, or frequency given (a) the research procedures that are described in the protocol-related documents, such as the Institutional Review Board (IRB)-approved research protocol and informed consent document; and (b) the characteristics of the participant population being studied;

• Related or possibly related to participation in the research ("possibly related" means there is a reasonable possibility that the incident, experience, or outcome may have been caused by the procedures involved in the research); and

FMT f	or FI
IRB#:	834196

• Suggests that the research places participants or others at a greater risk of harm (including physical, psychological, economic, or social harm) than was previously known or recognized.

